At the completion of at least 2 weeks of run-in (with a minimum of at least 8 rescue inhaler usages) and with documentation of stable clinical status throughout run-in, the patient will return for baseline testing; including vital signs, health related quality of life and Anthonisen Exacerbation questionnaires, pre and post bronchodilator spirometry and 6-minute walk testing (see table/flow chart). Average Peak Inspiratory Flow (Baseline PIF) and average Number of Rescue Inhalations per day (Baseline Inhalations) will be determined from the Digihaler Dashboard Data downloads during run-in.

In the event that the patient does not meet number of rescue inhaler usages or does not have a stable clinical status during run-in, an additional 2 weeks of run-in may be obtained. If at the end of the extended run-in period so that Baseline PIF and Baseline Inhalations cannot be determined or the patient continues to be clinically unstable, the patient will be discontinued from the study. If the patient has an upper respiratory tract infection or COPD exacerbation during run-in, they will also be discontinued from the study. Patients may be re-screened one time at a later date, when stable.

Once run-in and baseline testing are complete, all patients will continue on their maintenance COPD medications and use the ProAir Digihaler rescue SABA exclusively for the next 6 months. Patients will be provided with paper forms of the CAT, BCSS and Anthonisen Exacerbation criteria, to be completed at home on a weekly basis and mailed to the research center upon completion).

Throughout the treatment period, all rescue inhaler usage will be electronically transmitted to, monitored at and downloaded from the Digihaler Dashboard by the research center on every other business day basis (Monday, Wednesday and Friday). At the completion of each Digihaler Dashboard Data Download, comparisons of Daily PIF (average PIF of all rescue inhalations in a day) and Daily Inhalations (number of rescue inhalations in a day) to Baseline PIF and Baseline Inhalations will be made.

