All patients with Daily Inhalations exceeding Baseline Inhalations by ≥ 4 Inhalations per day and/or with a Daily PIF $\leq 80\%$ of Baseline PIF for 2 consecutive days will be DEFINED as “at risk”. For each “at risk” event, the patient will be contacted, their health status reviewed, and CAT and Anthonisen Exacerbation questionnaires will be administered. Based on symptoms, patients may also be advised to seek additional medical care.

All patients will be contacted on a monthly basis, irrespective of “risk” findings and seen in person every 3 months. All medication usage (including ProAir Digihaler medication usage), changes in medical care, healthcare contacts and usage, and any adverse events will be recorded. All office records for the intervening time period will be reviewed and Information for any non-office healthcare contacts and usage will be requested to provide detailed clinical information for comparison to Digihaler usage records.

At months 3 and 6 on treatment, all subjects will return to the research center, where vital signs, Anthonisen Exacerbation and CAT questionnaires, and post bronchodilator spirometry will be assessed. All medication usage (including ProAir Digihaler medication usage), changes in medical care, healthcare contacts and usage, and any adverse events will be recorded. All office records for the intervening time period will be reviewed and Information for any non-office healthcare contacts and usage will be requested to provide detailed clinical information for comparison to Digihaler usage records. Three (3) new ProAir Dihgihalers will be dispensed at month 3.

Throughout the treatment period, all rescue inhaler usage will be electronically monitored and downloaded from the Digihaler Dashboard by the research center on an every other business day basis (Monday, Wednesday and Friday). At the completion of each Digihaler Dashboard Data Download, comparisons of Daily PIF (average PIF of all rescue inhalations in a day) and Daily Inhalations (number of rescue inhalations in a day) to Baseline PIF and Baseline Inhalations will be made.

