- Determine timing of maintenance medication usage that morning will be recorded
- Administer 4 inhalations of albuterol via the ProAir Digihaler
- Perform post-bronchodilator Inspiratory Capacity (see testing)
- Perform post-bronchodilator Spirometry 20-30 minutes after albuterol dosing (see testing)
- Dispense 3 additional ProAir Digihalers and establish smartphone connectivity and internet access to the Digihaler Dashboard
- Instruction and training in the proper use of the ProAir Digihaler
- Provide paper copies of CAT, BCSS and Anthonisen Exacerbation criteria, to be completed at home on a weekly basis, along with instructions and stamped envelopes for questionnaire return upon completing
- Instruct patient to continue use of all maintenance medications
- Instruct patient to resume use of the original rescue inhaler(s) as needed
- Schedule 1-week safety telephone contacts

Months 1, 2, 4 and 5 Telephone Contact:

- Contact patient at scheduled date and time by telephone
- Review changes in health history, health care contacts, changes in medications, any healthcare utilization and any safety issues
- Review paper questionnaires submitted over the prior month
- Download Digihaler Dashboard Data
- Provide reminders and instructions, as needed.

Safety Telephone contact:

- Contact patients at scheduled date and time by telephone 1-week after visit 4
- Review patient health status and any safety issues that may have occurred after discontinuation of study medication

Testing

CAT questionnaire: (see appendix) will be self-administered at home on a weekly basis and at all clinic visits.

Anthonisen Exacerbation Criteria (AEC): (see appendix) will be self-administered at home on a weekly basis and at all clinic visits.

BCSS questionnaire: (see appendix) will be self-administered at home on a weekly basis and at all clinic visits.

mMRC questionnaire: (see appendix) will be self-administered at clinic visits 1 and 2.

Vitals signs, BMI, History, Physical Examination will be performed as per clinical standards.

Medication washout: Medication washout will occur prior to visit 2 as per the following:

SABA – 6 hours
SAMA – 6 hours
BID LABA or LABA/ICS – 12 hours
BID LAMA – 12 hours
BID LABA/LAMA/ICS – 12 hours
QD LABA or LABA/ICS – 24 hours
QD LAMA – 24 hours
QD LABA/LAMA/ICS – 24 hours

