7. Correlation and regression analysis of PIF and/or Inhalations events at varying thresholds
 - a. Daily PIF 10, 20, 30 or 40% below Baseline PIF
 - b. Daily Inhalations at 2, 4 or 6 Inhalations above Baseline Inhalations
 - c. Daily PIF and/or Inhalations duration of 2, 3 or 4 or more days outside of Baseline
8. Frequency and duration of AEC events of 2 or more major symptoms (Type I and Type II)
9. Frequency and duration of BCSS events (increase in BCSS by 2 above Baseline BCSS)
10. Correlation and regression analysis of PIF, Inhalations and IV events with AEC events
11. Correlation and regression analysis of PIF, Inhalations and IV events with BCSS event
12. Correlation of Digihaler changes in PIF above baseline and changes in CAT
13. Correlation off changes in SABA use above baseline with changes in CAT
14. Correlation of Digihaler changes in Inhalation Volume above baseline with changes in CAT
15. Descriptive sub-group analysis of PIF, Inhalations and IV thresholds by FEV1 severity, GOLD groups and BODE at Baseline.

REFERENCES

1. World Health Organization. Global Health Estimates 2016: Deaths by Cause, Age, Sex, by Country and by Region 2000–2016. 2018 [accessed October 2020]. s
2. GOLD. Global Strategy for the Diagnosis, Management, and Prevention of Chronic Obstructive Pulmonary Disease. 2020 Report. www.goldcopd.org.
3. Nici L, et al. Pharmacologic Management of Chronic Obstructive Pulmonary Disease. An Official American Thoracic Society Clinical Practice Guideline Am J Respir Crit Care Med. 2020; 201:56-59.
7. van der Molen T, Miravitles M, Kocks JW. COPD management: role of symptom assessment in routine clinical practice. Int J Chron Obstruct Pulmon Dis. 2013; 8:461-471.

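### Planned durations of AEC and BCSS events rest mainly on weekly forms, so they are known only to about a week at each end, and their order against daily device changes is often unresolved at lags under a week

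*Protocol*

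**What the plan says.** In the protocol's Planned Analysis, item 8 is "Frequency and duration of AEC events of 2 or more major symptoms (Type I and Type II") and item 9 is "Frequency and duration of BCSS events (increase in BCSS by 2 above Baseline BCSS"). Items 10 and 11 correlate and regress device events (PIF, inhalations, inhalation volume) with AEC and BCSS events. Item 6 does the same with CAT events.

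The Protocol Overview supplies the symptom forms on paper, "to be completed at home on a weekly basis and mailed to the research center upon completion". The Testing section repeats the schedule: "Anthonisen Exacerbation Criteria (AEC): (see appendix) will be self-administered at home on a weekly basis and at all clinic visits", and "BCSS questionnaire: (see appendix) will be self-administered at home on a weekly basis and at all clinic visits".

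There is one event-driven source, described in the Protocol Overview: "For each “at risk” event, the patient will be contacted, their health status reviewed, and CAT and Anthonisen Exacerbation questionnaires will be administered". BCSS is not part of that contact.

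Device values are daily and are downloaded on Monday, Wednesday and Friday. Item 7c varies the device event: "Daily PIF and/or Inhalations duration of 2, 3 or 4 or more days outside of Baseline". These are minimum lengths.

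The protocol gives no rule for the start or end date of an AEC or BCSS event.

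**The concern.** A duration needs a start and an end. With one observation a week, each end is known only to lie somewhere between two forms. A duration reported in days would therefore largely reflect the weekly grid. If forms describe a single day, episodes shorter than a week are also caught more often the longer they last, so recorded events lean towards the longer ones.

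The same coarseness affects items 6, 10 and 11. The study hopes to find device thresholds that mark deterioration, and a reader of the results will want to know whether the device change came before or after the symptom change. When the two are less than a week apart, the weekly forms often cannot show this.

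The 'at risk' AEC adds a further difficulty. It is given because the device signal crossed a limit, so AEC is looked for more closely around device events than elsewhere. Item 10 then correlates AEC with those same device events.

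**Working it through.** The protocol states no figure for this point, so there is nothing to reproduce. The check is sampling-interval arithmetic.

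**Inputs from the protocol.** Home forms every 7 days (Protocol Overview, Testing). Daily device data, downloaded Monday, Wednesday and Friday (Protocol Overview). CAT and AEC at each 'at risk' contact, triggered by at least 4 inhalations above baseline and/or a daily PIF at or below 80% of baseline for 2 consecutive days.

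**Assumptions.** A form describes the day it is completed. Forms are exactly 7 days apart and none is missing. Their timing is unrelated to the events.

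**1. Duration bounds.** For k consecutive positive forms with a negative form on each side, the true duration lies between 7(k−1) and 7(k+1) days.
- k = 1: above 0 and below 14 days.
- k = 2: 7 to 21 days.
- k = 3: 14 to 28 days.

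Each missing neighbouring form adds 7 days to the upper bound.

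**2. Chance that an episode meets a form.** For an episode of d days this is min(1, d/7): 2/7 = 29%, 3/7 = 43%, 4/7 = 57%, and 100% from 7 days on. The short values of d are illustrative; the protocol does not say how long AEC or BCSS episodes last.

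**3. Order of two onsets L days apart, weekly forms only.** The order is shown if a form falls between them, with probability min(1, L/7).

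| L (days) | 1 | 2 | 3 | 4 | 5 | 7 or more |
|---|---|---|---|---|---|---|
| Order shown | 14% | 29% | 43% | 57% | 71% | 100% |

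**4. What the 'at risk' AEC adds.** Assume the contact takes place at the first download after the second event day is over. For device onset on Monday to Sunday the delays are 2, 3, 2, 4, 3, 2 and 3 days, mean 19/7 = 2.7. If the device change comes first by L days, the contact finds a negative AEC when the delay is shorter than L. The order is then shown with probability 1 − (1 − L/7)(1 − P), where P is the chance that the delay is below L.
- L = 1 or 2: P = 0, no gain.
- L = 3: P = 3/7, so 1 − (4/7)(4/7) = 33/49 = 67%.
- L = 4: P = 6/7, so 1 − (3/7)(1/7) = 46/49 = 94%.
- L = 5: P = 1, so 100%.

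If the contact may fall on the second event day itself, the delays are 2, 1, 2, 1, 3, 2 and 1 days. The values become 14% at L = 1, 1 − (5/7)(4/7) = 59% at L = 2, 1 − (4/7)(1/7) = 92% at L = 3, and 100% at L = 4.

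Under either assumption nothing is gained when symptoms come first, because a positive AEC after the device change does not show when the worsening began. Nothing is gained for BCSS, nor for device events that do not trigger a contact, such as a 10% PIF fall, 2 extra inhalations, or inhalation volume alone.

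**5. If the form instead covers the whole past week.** Every episode then falls within some form's window, so step 2 no longer limits detection. An episode touching k windows lasts more than 7(k−2) and at most 7k days: up to 7 days for one form, above 0 and up to 14 for two. Onset is still known only to a 7-day window, so step 3 is unchanged.

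**The case against.** Much can be said for the plan.

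- **Other sources exist.** A reader might infer that symptom worsening is dated by the weekly form alone. That is not so. AEC and CAT are also given at every 'at risk' contact, and forms are completed at clinic visits. The adverse event section records deterioration as an adverse event, with times of onset and resolution. This stands, with limits: the contacts are device-triggered, adverse events are gathered mainly at monthly calls, and items 8 to 11 are defined on AEC and BCSS, not on adverse events.
- **The forms are not shown.** Their appendix may set a recall period or already ask for dates. This stands, so the detection figures and the bounds are conditional.
- **Device events are not short by definition.** Item 7c might be read as saying that they last 2 to 4 days. The wording sets minimum lengths.
- **The objectives concern association.** The exploratory objectives speak of concomitant measurement, and the protocol disclaims power and expected predictive probabilities. Lead time is not a stated aim, so a before-and-after display is an addition and its absence is not an error.
- **A late signal can still help.** One might infer that a PIF fall following symptoms is worthless for identifying deterioration. The Background says that over half of exacerbations are never reported and that patients often delay reporting. A signal that precedes the report would still serve the stated purpose.
- **Matching windows may sit in the SAP.** This stands for windows and lag rules. It does not stand for onset and end dates: if they are not collected, no later plan can supply them.

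**Conclusion.** The point holds in a limited form. AEC and BCSS durations carry about a week of uncertainty at each end. On completion-day forms, one positive form is compatible with anything above 0 and below 14 days; with seven-day recall, with anything up to 7 days. For onsets less than a week apart, the weekly forms often leave the order open (43% resolved at 3 days). The 'at risk' AEC raises that to between 67% and 92% when the device change comes first, and not at all when symptoms come first. BCSS, which has no triggered administration, is the weaker of the two.

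It would be too much to say that these durations or the time order cannot be measured. Durations are interval-bounded, and order is resolved at lags of 7 days or more. The figures rest on regular, complete forms whose timing is independent of events. The point touches mainly exploratory outcomes and is minor.

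**What to change.** 1. Unless the appendix form already asks for them, add two dates to the weekly AEC form and to the 'at risk' call record: when the worsening began and when the patient was back to usual. Compute AEC duration from these dates.
2. Report BCSS duration, and any AEC duration without dates, as the number of consecutive positive forms with its lower and upper bounds, not in days.
3. In item 10, and in items 6 and 11 where an AEC onset date exists, show device data before and after that onset separately, as an added descriptive analysis.
4. Show scheduled and device-triggered AECs separately, so that the closer observation around device events is visible.

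The cost is two lines on a form and on the call record, slightly more data entry, and up to a week of recall error in the dates. The protocol's front page gives a study period of May 2021 to June 2022. If collection has closed, items 2 and 4 can still be adopted, and item 3 wherever an onset date was recorded.

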- 2) Describe specific ProAir Digihaler SABA inhalations per day (Inhalations) above baseline (e.g. 2, 4 or 6 inhalations/day for a minimum of 2 consecutive days) to identify an optimal threshold for characterizing trends in acute changes in the CAT
- 3) Describe specific changes in ProAir Digihaler Inhalation Volume (IV) (e.g. 10, 20, or 30% reduction in IV from baseline for a minimum of 2 consecutive days) to identify an optimal threshold for characterizing trends in acute changes in the CAT

Exploratory Objectives:

- 1) Determine whether ProAir Digihaler changes in PIF and in SABA use above baseline thresholds are influenced by baseline COPD condition, as measured by:
 - a) COPD Assessment Test (CAT)
 - b) Modified Medical Research Council Dyspnea Scale (mMRC)
 - c) GOLD group [A-D]
 - d) FEV₁ severity/GOLD grade [I-IV]5)
 - e) BODE score [Body Mass Index (BMI), Airway Obstruction (FEV₁), Dyspnea (mMRC), and Exercise Tolerance (6-minute walk)]
- 2) Determine if concomitant measurement of Anthonisen Exacerbation Criteria (dyspnea, sputum amount and color change) using the Breathlessness, Cough and Sputum Survey (BCSS) is associated with ProAir Digihaler changes in PIF below baseline thresholds
- 3) Determine if concomitant measurement of Anthonisen exacerbation criteria (dyspnea, sputum amount and color change) using the Breathlessness, Cough and Sputum Survey (BCSS) is associated with ProAir Digihaler changes in SABA use above baseline thresholds
- 4) Determine if concomitant measurement of Anthonisen exacerbation criteria (dyspnea, sputum amount and color change) using the Breathlessness, Cough and Sputum Survey (BCSS) is associated with ProAir Digihaler changes in Inspiratory Volume below baseline thresholds
- 5) Determine if Inspiratory Capacity (IC) correlates to Inhalation Volume (IV) measured by the ProAir Digihaler, at baseline and during the study

Primary Outcome Measure:

- 1) Change in Peak Inspiratory Flow (PIF) from Baseline as measured via the ProAir Digihaler device

Secondary Outcome Measures:

1. Change in SABA use (Inhalations) from Baseline
2. Change in Inhalation Volume (IV) use from Baseline
3. Change in CAT
4. Change in FEV₁

Other Outcome Measures:

1. Change in Anthonisen Exacerbation Criteria
2. Change in BCSS
3. Change in Inhalation Volume

Trial Population Entry Criteria:**Inclusion Criteria:**

- 1) Documented history of COPD by ATS/GOLD criteria
- 2) Age > 45 years
- 3) Patient willing and able to:

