The number of albuterol rescue inhalations used and measured over 2 weeks at baseline using the Digihaler device. Baseline inhalations per day at baseline will be derived by the total number of inhalations divided by the total number of days during the baseline period and reported as inhalations per day or Baseline Inhalations/day.
3. Baseline Inhalation Volume (**Baseline IV**) measured via Digihaler device
IV is the volume of air inhaled during an albuterol rescue inhalation effort, expressed in Liters. Individual IV measurements collected over 2 weeks at baseline will be measured using the Digihaler device. The mean value for IV during the baseline period will be reported as the Baseline IV.

Protocol Overview

The trial is an unblinded open label single center study designed to identify trends in Peak Inspiratory Flow (PIF) rates and Rescue Albuterol Inhaler usage (Inhalations) that associate with disease deterioration as defined by worsening of symptoms and reduced lung function in patients with COPD.

The study will consist of a run-in period of approximately 2 weeks, a treatment period of 6 months and a follow-up period of 1 week. Twenty (20) patients with COPD requiring intermittent short acting beta agonist (SABA) rescue inhaler usage, but not requiring frequent SABA nebulizer rescue usage, will be enrolled.

After signing informed consent, patients will undergo a screening evaluation. During the run-in period, patients will continue on their COPD maintenance treatments, while discontinuing all previously prescribed periodic use rescue medications. Upon completion of screening, all patients will be dispensed a ProAir Digihaler to be used exclusively as their rescue medication throughout the duration of the study. During the run-in period all rescue inhaler usage will be electronically monitored and patient data from the Digihaler Dashboard will be downloaded every other business day basis (Monday, Wednesday and Friday).

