If a serious adverse event occurs, the Institutional IRB will be notified within five business days of awareness of the event by the investigator. The study coordinator may initiate the IRB notification, but it must be filed by the study investigator or co-investigators. If the serious adverse event is fatal or life threatening, notification to the Institutional IRB must be made within 24 hours, irrespective of the extent of available adverse event information. This timeframe also applies to additional new information (follow-up) on previously forwarded serious adverse event reports.

The MedWatch 3500A form should be utilized to report serious adverse events to the FDA.

All adverse events (serious and non-serious) will be reported on the adverse event page(s) of the CRF. Adverse events should be reported using concise medical terminology on the CRFs. Non-serious AE's will be reported annually to the IRB as appropriate.

STATISTICAL ANALYSIS

Primary Outcome Measure:

- 1) Change in Peak Inspiratory Flow (PIF) from Baseline as measured via the ProAir Dihaler device

Secondary Outcome Measures:

1. Change in SABA use (Inhalations) from Baseline
2. Change in Inhalation Volume (IV) from Baseline
3. Change in CAT
4. Change in FEV₁

Other Outcome Measures:

1. Change in Anthonisen Exacerbation Criteria
2. Change in BCSS
3. Change in Inhalation Volume

All data is exploratory, with no calculated power or expected predictive probabilities. Statistical thresholds, comparisons, correlations and regressions, sensitivity/specificity/ROC analysis will be performed using Wizard 1.9.45 Statistics. Additional statistical analysis may be performed as per TEVA biostatistics.

PLANNED ANALYSIS

1. Average of PIF value and number of PIF events at 10%, 20%, 30%, 40% below Baseline PIF for 2 or more days per patient
2. Average summary statistics PIF values and frequency of PIF events across all patients
3. Number of inhalations per day that are 4 or more Inhalations above Baseline Inhalations for 2 or more days
4. Frequency of IV events that are 20% below Baseline (see Derived measurements) for 2 or more days
4. Frequency of combined events of PIF and IV 20% below Baseline and 4 or more Inhalations per day above Baseline for 2 or more days combined
5. Frequency of CAT events (defined as increase in CAT score by 2 above Baseline CAT score)
6. Correlation and regression analysis of PIF, Inhalations and IV events with CAT events

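### BCSS is related to the device data only as a +2 event (item 11); the listed outcome, change in BCSS score, has no association analysis such as CAT is given in items 12 to 14

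*Protocol*

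**What the plan says.** All references are to the protocol, the only document available.

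- **Objectives.** Exploratory Objectives 2 to 4 ask whether the Anthonisen criteria, measured "using the Breathlessness, Cough and Sputum Survey (BCSS) is associated with ProAir Digihaler changes in PIF below baseline thresholds", and likewise for SABA use above and inspiratory volume below baseline thresholds. The threshold is on the device variable. No cut is stated for the BCSS.
- **Outcome.** Other Outcome Measure 2 is "Change in BCSS", listed separately from change in the Anthonisen criteria. Under Testing, the BCSS is completed at home every week and at all clinic visits.
- **Planned analysis.** The BCSS appears in two items. Item 9 is "Frequency and duration of BCSS events (increase in BCSS by 2 above Baseline BCSS"). Item 11 is "Correlation and regression analysis of PIF, Inhalations and IV events with BCSS event".
- **CAT, for comparison.** Item 6 relates device events to CAT events. Items 12 to 14 then correlate changes in PIF, SABA use and inhalation volume with changes in CAT; item 13, for example, reads "Correlation off changes in SABA use above baseline with changes in CAT".
- **Size and status.** The Protocol Overview plans "Twenty (20) patients with COPD requiring intermittent short acting beta agonist (SABA) rescue inhaler usage" and "a treatment period of 6 months". The Statistical Analysis section says "All data is exploratory, with no calculated power or expected predictive probabilities".

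**The concern.** The listed outcome is a change in score, but no listed item relates that score to the device. In item 11 a rise of 1 counts the same as no change, and a rise of 6 the same as a rise of 2. CAT, collected on the same weekly schedule, is analysed both as an event and as a change, and no reason is given for treating BCSS differently. The objectives that look for an optimal threshold concern CAT, so they do not call for a BCSS cut.

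With 20 patients and device events that may be infrequent, an event-with-event comparison can easily miss an association that the forms already collected could show. This is more than detail left to a statistical analysis plan, because the protocol itself fixes both the event definition and the analysis that uses it.

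**Working it through.** The plan states no power, effect size, SD or event rate, so there is no figure to reproduce. The check therefore asks what the BCSS cut costs under stated assumptions.

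**Inputs from the protocol.** 20 patients; 6 months of weekly forms, about 26 each, so 20 × 26 = 520 correlated patient-weeks if all are returned; a BCSS event at +2; a PIF event at 20% below Baseline (one of the planned thresholds).

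**Assumptions, not from the protocol.** Within-patient SD of PIF 12–15% and of BCSS change 1.5–2 points; weekly autocorrelation 0.4; correlation rho between PIF fall and BCSS change of 0.15–0.20; two-sided 5% test.

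**Step 1: information kept when the BCSS alone is cut.** For a weak linear-normal association, the share kept is φ(z_p)² / [p(1 − p)], where p is the share of weeks with an event.

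- p = 0.5: 0.399² / 0.25 = 64%
- p = 0.2: 0.280² / 0.16 = 49%
- p = 0.1: 0.1755² / 0.09 = 34%
- p = 0.05: 0.1031² / 0.0475 = 22%

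The loss from cutting the BCSS is thus 36–78%, and exceeds one half only when events fill about 20% of weeks or fewer. With the assumed SDs and whole-point scores, a +2 event means an underlying change of at least 1.5. That is P(Z > 1.5/1.5) = 16% to P(Z > 1.5/2) = 23% of weeks. A 20% PIF event is P(Z > 20/12) = 5% to P(Z > 20/15) = 9% of weeks.

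**Step 2: simulated power, linear relation.** 20 patients × 26 weeks, values centred within patient, one cross-product per patient, t-test on 19 df, 1,500 runs per setting. The 20% PIF event is kept in both columns.

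| rho | PIF SD / BCSS SD | PIF event with +2 BCSS event | PIF event with BCSS score |
|---|---|---|---|
| 0.15 | 12% / 1.5 | 9% | 26% |
| 0.15 | 15% / 2 | 19% | 39% |
| 0.20 | 12% / 1.5 | 14% | 41% |
| 0.20 | 15% / 2 | 33% | 58% |

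Repeat runs agree within a few points, giving overall ranges of about 8–33% and about 24–59% (one run gave 22% at the low end). Rejection under no association was 4–8%. A setting with SDs of 10% and 1.2 is left out because the event-with-event test rejected 23% of the time under no association.

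**Step 3: simulated power, episodic deterioration.** Here PIF and BCSS are unrelated except in occasional bad weeks. With 3% of weeks having a 25% PIF fall and +3 BCSS, the score gives 58% and the +2 event 54%. With 5% of weeks at 20% and +2, the figures are 51% and 41%. With milder episodes they are 26% and 19%. The gains are 4, 10 and 7 points. Repeat runs ranged from 2 points (59% against 57%) to 14 (52% against 38%). The score matched or beat the +2 event in every setting run.

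**The case against.** The strongest points on the other side are these.

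- **The target is exacerbation.** Objectives 2 to 4 name the Anthonisen criteria, so a symptom event is a natural endpoint, and the planned sensitivity/specificity and ROC work needs a binary reference. This stands as a reason to keep items 9 and 11. It is no reason to leave the separately listed change score without an association analysis.
- **Device thresholds are intended.** A reader might compare full-scale PIF and full-scale BCSS (76–78% power at rho 0.15) with the event-with-event analysis (9–19%) and conclude that the plan throws away most of its power. That contrast also removes the device threshold the objectives ask for, so it is not like for like. Nor should a full-scale analysis become the main one: in the first episodic case it reached only 46%, below the 54% of the event-with-event analysis.
- **The simulation simplifies.** The protocol's device events need 2 or more days, PIF exists only on days of rescue use, and complete weeks were assumed. Inhalations and volume were not simulated. This stands: the figures illustrate and do not predict.
- **Events need not be yes/no.** Other items count the number, frequency or duration of events, so item 11 might relate counts. That would soften the device-side loss but would still not use the BCSS score.
- **The +2 cut may have a source.** The reference list includes a paper on interpreting the BCSS. It is not tied to item 9 and could not be read here, so the cut is not called unjustified.
- **The trial is exploratory and further analyses are allowed.** This lowers the stakes. There is no decision rule by which the trial would formally conclude that no link exists. But permission for unspecified further analyses leaves the score analysis optional and unplanned.

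**Conclusion.** The point holds on the BCSS side. Item 11 is the only planned link between BCSS and the device, it uses BCSS only as a +2 event, and the change-based analysis given to CAT is missing although change in BCSS is a listed outcome. Under the linear assumptions the BCSS score adds roughly 17 to 27 points of power against the same 20% PIF event (26 − 9 = 17; 41 − 14 = 27). Under episodic deterioration it adds roughly 4 to 10.

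The documents give no correlation, SD or event rate to choose between these, so they support neither a statement that most of the power is lost nor a prediction that the trial will miss a real association. This is a cheap improvement, not an error that undermines the study.

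**What to change.** For Exploratory Objectives 2 to 4:

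1. Add to item 11 an analysis of change in BCSS score from Baseline against the threshold-defined PIF, Inhalations and IV events, with a model that allows for repeated weeks within a patient (for example, a patient-level random effect or patient-clustered standard errors).
2. Add correlations of change in BCSS with changes in PIF, Inhalations and IV, parallel to items 12 to 14 and allowing for the same repetition.
3. Keep items 9 and 11 as the event-based analysis.

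The cost is a few lines of text and a few more model runs on forms already collected, with no new visits, patients or measurements. The downside is a few more exploratory results to report.
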